5.2 Recruitment Methods

Given the scope of the proposed study, a total sample size of 40 veterans is considered a realistic and achievable enrollment to generate pilot data. For AIM 1, a cross-sectional design that includes within-subjects (VETS conditions) and between-subjects (veteran groups) factors will be used to compare balance and posture in patients awaiting surgery for CSM ($n = 20$) to a cohort of age and gender-matched non-CSM controls ($n = 20$). The 20 veterans with CSM recruited for AIM 1 will also serve as the sample for AIM 2, which is a longitudinal assessment of balance following surgical intervention for CSM.

Drs. [name], [name] and [name] will identify potential participants for the CSM group by screening all CSM patients undergoing assessment and scheduling for surgical intervention. These potential participants will be referred to [name] study team, where a staff member will provide background information, additional pre-screening, and scheduling (if eligible and interested).

Healthy volunteers will be recruited using a poster/flyer within the SVAMC. Potentially interested participants will call the study staff, as prompted by the advertisement, and will undergo pre-screening and scheduling. A copy of this flyer may be found in the submission package. Healthy volunteers may also be recruited from the pool of participants who consented to future contact in the SMBI Data Repository. These individuals will be contacted by the research staff and will be asked if they are interested; the attached Telephone Script includes the language used for these participants.

For the cross-sectional arm of the study, veteran volunteers in the CSM and control conditions will be compensated \$40 for their participation. Veteran volunteers in the CSM group will have the opportunity to earn an additional \$40 for attending each of the three post-operative assessments, resulting in a maximum remuneration of \$160. Participants will be paid in full for all sessions attended, even if they cease participation before fully completing a session. Payment will be sent in the form of a VA check to the address specified by the participant.

5.3 Informed Consent Procedures

Before the start of the testing session, the experimenter (the PI or a designated member of the research staff) will review the consent form with the participant and any study-related questions will be answered. This will take place in a private office. Participants will be encouraged to take their time and read the form carefully and in its entirety before they sign. Should the participant wish to take the consent form to review and think over, they will be permitted to do so. The participant's consent about his/her comprehension of the experiment and his/her willingness to participate will be obtained. The participant will also check a box indicating whether or not they consent to having their data stored in a research repository. Additionally, optional consent for recontacting will be requested. The participant will sign the form in front of the experimenter, indicating that they have read and understood all portions of the consent form, and the experimenter has answered any and all questions the participant had about the research of their participation. The same process will be followed for HIPAA authorization. The participant will be provided with a copy of the consent form and a copy of the signed HIPAA authorization form.

5.4 Inclusion/Exclusion Criteria

Inclusion criteria for the CSM group are:

- Symptoms of myelopathy in upper and lower extremities and stenosis of the cervical spine demonstrated by MRI or myelography
- Lower extremity muscle strength of 4 as quantified by manual muscle test (MMT) or above
- Ability to stand without support with eyes closed for 30 seconds or more.

Exclusion criteria for all study participants are:

- History of neurological disorder other than lumbar spine disease or peripheral neuropathy
- Inability to stand in an upright position with both feet together and eyes closed.

Veterans in the control group will be recruited via printed advertisement or through the SMBI Data Repository and age- and sex-matched with CSM veterans. Every effort will be made to ensure that the veteran participants enrolled in the proposed study are reflective of the VA population, with regard to sex and race/ethnicity. If any participant over the age of 89 happens to enroll, their exact age will be recorded as >89.

5.5 Study Evaluations

A. Materials

Scale Measures. Measures to be used in the proposed study include the modified Japanese Orthopaedic Association (mJOA) scale, the Nurick Scale, Neck Disability Index (NDI), and Short Form-36 (SF-36). The mJOA and Nurick Scale will be completed by one of the study team doctors during clinical visits, and the NDI and SF-36 will be completed by the participant. Participants will also fill out a demographics questionnaire once.

Modified Japanese Orthopaedic Association (mJOA) scale ¹⁷. The mJOA is an instrument used to assess motor dysfunction of the upper and lower extremities, sensory loss of the upper extremity, and sphincter dysfunction. Motor dysfunction of the upper extremities is assessed on a 6-point Likert scale, with values ranging from 0 (inability to move hands) to 5 (no dysfunction). Motor dysfunction of the lower extremity is assessed on an 8-point Likert scale, with values ranging from 0 (complete loss of motor and sensory function) to 7 (no dysfunction). Sensory dysfunction of the upper extremities is assessed on a 4-point Likert scale, with values ranging from 0 (complete loss of hand sensation) to 3 (no sensory loss). Finally, sphincter dysfunction is assessed on a 4-point Likert scale, with values ranging from 0 (inability to micturate voluntarily) to 3 (normal micturation).

Nurick Scale ¹⁵. The Nurick scale is a 6-grade ordinal scale assessing gait impairment, with grades ranging from 0 (signs and symptoms of root involvement but no evidence of spinal cord disease) to 5 (chair bound or bedridden).

Neck Disability Index (NDI) ¹⁶. The NDI is a 10-item self-report questionnaire addressing function activities (personal care, lifting, reading, work, driving, sleeping, and recreation), pain intensity, concentration, and headache. For each item, patients make their ratings on a 6-point Likert scale with values 0 = no disability and 5 = complete disability. Summed scores for each category are multiplied by 2 to give a total NDI score ranging from 0-100.

Short Form-36 (SF-36) ³⁷. The SF-36 is a self-report general health survey that includes mental and physical component scores to measure functional status and overall quality of life. The instrument includes 8 scales: physical functioning, role limitations physical pain, bodily pain, general health perceptions, vitality, social functioning, role limitations, emotional health, and mental health.

Demographics: The demographics form will ask about basic information, including: age, sex, history of head injury, and current medications.

VETS. Postural stability will be assessed with the VETS system devised by [name] ^{31, 38-40}. All postural conditions are performed in a darkened room. The physical set-up has the front edge of the Wii balance board (WBB) placed at a distance of 40 cm from a 60" commercially-available flat screen television. This device employs a custom-designed software user interface that allows wireless Bluetooth collection of

center-of-pressure data at 100 Hz with high test-retest reliability and immediate display of results. Excellent concurrent validity was determined by comparing VETS with a research grade gold-standard NeuroCom, which revealed $ICC > 0.90$ (min: 0.901, max: 0.995, $p < 0.01$).

The postural stability task will involve six conditions during which veterans are instructed to look straight ahead and maintain an upright stance as stably as possible (see Figure 2). Veterans are barefooted with feet comfortably placed ~25 cm apart. The six conditions are (1) Eyes Open (EO) Firm – eyes open with stable support surface (i.e. WBB) and static visual scene, (2) Eyes Closed (EC) Firm – eyes closed with stable support surface and dark screen, (3) Dynamic Scene (DYN) Firm – eyes open with a stable support surface while viewing a scene dynamically rotating in the roll (fronto-parallel) plane at 60 deg/s, (4) EO Foam - eyes open with unstable support (Airex foam pad placed on top of the WBB) and stable visual scene, (5) EC Foam – eyes closed with unstable support and dark screen, and (6) DYN Foam – eyes open with unstable support and rotating scene. Each condition lasts 30 secs and is repeated 3 times before progressing to the next condition. The conditions are tested in order 1-6, in a manner that emulates the validated Sensory Organization Test (SOT) protocol (Natus/Neurocom). For safety, an experimenter guards the veteran to protect against falls.

B. Procedure

Initial Testing Session: For all participants, the first session will involve obtaining informed consent and HIPAA authorization, completing self-report questionnaires, and a session of VETS testing. This initial session will last approximately 60 minutes. The informed consent procedure will follow the description outlined in section 5.3 and is expected to take around 15 minutes. Subsequently, the participant will fill out all listed self-report questionnaires, which will take about 15 minutes. Lastly, the participant will undergo one session of VETS testing, which will take about 20 minutes. VETS testing will follow the protocol outlined above in the “Materials” section. For CSM patients, one of the study doctors will fill out the clinical assessments during standard of care appointments throughout the study that correspond in time with the participant’s research appointments.

All subsequent sessions (2, 3, & 4) will include CSM participants only, and will be conducted after surgical treatment.

Testing Session 2: Participants will be scheduled for the second testing session 2 weeks post-surgery. This session will include all self-report questionnaires except demographics and a session of VETS testing. It will last approximately 30-45 minutes.

Testing Session 3: Participants will be scheduled for the second testing session 6 weeks post-surgery. This session will include all self-report questionnaires except demographics and a session of VETS testing.

Testing Session 4: Participants will be scheduled for the second testing session 6 months post-surgery. This session will include all self-report questionnaires except demographics and a session of VETS testing.

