Study of Postural Stability in Subjects with Myelopathy using a Portable Virtual Reality Balance Protocol

NCT03810781

Principal Investigator: [name]

Version Date: 9/5/19

Abstract

Veterans are at heightened risk of developing cervical spondylotic myelopathy (CSM) from rigors of military service. Diagnosis of CSM involves a set of clinical findings and is confirmed by imaging the spine.

Gait impairment and disturbances of stance control are hallmarks of CSM and are a consequence of abnormalities in proprioception due to dorsal column tract damage of the spine. Currently, gait and balance deficits rely on clinical level assessments and judgement for detection. An objective measure of posturography has the benefit of: a) quantifying balance-related disability in CSM, b) facilitating structure-functional assessments in CSM, and c) quantifying the degree surgical interventions affect posturography and recovery of function in CSM.

Objective and sensitive means for assessing balance and posturography exist, but are not routinely incorporated in diagnosis or functional tracking of progress after interventions such as surgery. A barrier may be accessibility of posturography and ease of assessments. The Virtual Environment TBI Screen (VETS) was devised using Army Rapid Innovation Development funding to objectively assess balance and posturography in a cost effective, but sensitive manner. VETS involves virtual environments and computerized posturography and is proving to be a sensitive system facilitating diagnosis, treatment, and mitigation of balance dysfunction associated with mTBI.

Our working hypothesis is VETS testing will enhance clinical judgements regarding CSM. This study is designed to provide data critical to a more extensive program of research incorporating posturography into treatment and rehabilitation of CSM. First, a limited comparative study of standing balance will be conducted of 20 veterans being evaluated for cervical spine surgery to treat CSM and 20 otherwise healthy veterans. Second, posturography of the 20 veterans undergoing surgery to treat CSM will be tracked during their scheduled follow up visits to determine the degree VETS scores are affected by surgery and to track recovery from CSM.

List of Abbreviations

ALS	amyotrophic lateral sclerosis
ANOVA	analysis of variance
AUC	area under the curve
COP	center of pressure
CSM	cervical spondylotic myelopathy
CT	computed tomography
DYN	Dynamic
EC	Eyes Closed
EO	Eyes Open

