3.0 Objectives

AIM 1A: Determine whether and to what degree balance is altered in CSM. The degree of COP sway will be compared between CSM and controls in the six conditions comprising VETS testing.

Hypothesis 1: Impaired proprioceptive transmission in CSM will result in poorer balance (larger COP sway area) during EC conditions (eliminating the ability to compensate with visual feedback) and FOAM (reducing the reliability of somatosensory feedback) conditions compared to healthy veterans.

AIM 1B: Determine whether VETS enhances sensitivity and selectivity in the diagnosis of CSM. Composite measures of balance will be related to clinical assessment tools and their relationship with MRI.

Hypothesis 2: VETS will provide additional sensitivity and selectivity in identifying CSM compared to current clinical assessment tools.

Hypothesis 3: The degree of COP sway area during EC and FOAM conditions is expected to directly relate to the degree of spinal cord compression quantified from MRI, leading to a more sensitive gradation in the severity of CSM.

AIM 2: Evaluate the VETS scores after surgery for CSM. The degree of COP sway area under the 6 conditions will be compared before surgery, 2 weeks, 6 weeks, and 6 months after surgery.

Hypothesis 4: We expect surgery to reduce COP sway in EC conditions

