5.0 Study Procedures

5.1 Study Design

For AIM 1, a cross-sectional design that includes within-subjects (VETS conditions) and between-subjects (veteran groups) factors will be used to compare balance and posture in patients awaiting surgery for CSM ($n = 20$) to a cohort of age and gender-matched non-CSM controls ($n = 20$). The 20 veterans with CSM recruited for AIM 1 will also serve as the sample for AIM 2, which is a longitudinal assessment of balance following surgical intervention for CSM. The data generated from the proposed study will provide a base estimate of the variance in our veteran groups for use in the power calculation for a larger follow up study

Veteran volunteers (CSM and control) meeting eligibility criteria will complete one session of VETS balance testing. Those veterans awaiting surgery for CSM will be asked to return for three additional sessions of VETS at designated time points scheduled 2 weeks, 6 weeks, and 6 months post-surgery. For returning CSM veterans, self-report measures will be collected at each additional time point to compare objective (VETS) and subjective (scale measures) assessments of functional impairment related to CSM following surgery. None of the procedures involved in this research project will alter standard of care associated with CSM or the surgical treatment. “Each patient will be cleared by one of the study doctors ([name], [name], or [name]) before participating in the post-surgery sessions. In the event that a patient is found to be physically incapable of safely participating in the first post-surgery session, they will not continue participation in the study until they are cleared by the study doctors. Thus, even if a patient is not cleared to participate in the two week post-surgery time point, they may be cleared to participate in the remaining two sessions (six weeks and six months post-surgery).”

Risks/Benefits of Participation

There are no risks associated with the questionnaires included in this study, as they ask only about physical symptoms and functioning associated with CSM. Although some emotional health questions will be included, they are not expected to be upsetting in any capacity.

The risks associated with VETS testing are minimal and are as follows:

- Discomfort from standing on the WBB or foam for a prolonged period of time
- Dizziness or disorientation when viewing the dynamic condition

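### Aim 2 retests only operated patients, so it can describe change in VETS scores after surgery but cannot attribute that change to surgery, as the Abstract and Hypothesis 4 do

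*Combined protocol and SAP*

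**What the plan says.** Two places attribute change to surgery. The Abstract gives the purpose of the follow-up as "to determine the degree VETS scores are affected by surgery and to track recovery from CSM". Hypothesis 4 in section 3.0 reads "We expect surgery to reduce COP sway in EC conditions".

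Other text is descriptive. Aim 2 in 3.0 is a comparison of sway area before surgery with three later times, and 5.6 calls its target within-group change over time.

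On who is tested and when, 5.1 says "Veteran volunteers (CSM and control) meeting eligibility criteria will complete one session of VETS balance testing". CSM patients are then asked back for "three additional sessions of VETS at designated time points scheduled 2 weeks, 6 weeks, and 6 months post-surgery". Section 5.5 confirms: "All subsequent sessions (2, 3, & 4) will include CSM participants only", and it places all three after surgery. The sample is fixed in 5.1: "The 20 veterans with CSM recruited for AIM 1 will also serve as the sample for AIM 2".

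The Aim 2 analysis in 5.6 is a repeated-measures ANOVA in the CSM group, with time point added to the repeated factors. The text describes no retest of controls, no non-operated CSM group, no practice session, no second pre-surgery baseline and no caveat about attribution.

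**The concern.** Each CSM patient meets the foam, the dark room and the rotating scene four times. The first exposure is before surgery and the other three are after it. Each control meets them once. Within the Aim 2 data, after surgery and tested before are the same variable. If sway falls because the task has become familiar, the fall enters the time effect exactly as a surgical effect would. If sway rises because the disease progresses, that rise is netted against any benefit.

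What is at stake is the sentence the study can write at the end. Under the causal wording, a change over time would be reported as the effect of surgery, and the absence of change as the absence of an effect. Neither follows. The result is also meant to feed a larger research programme, so the attribution could carry forward.

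**Working it through.** **No figure to reproduce.** The plan gives no effect size, SD, test-retest coefficient or power for Aim 2. Section 5.5 calls retest reliability high without a coefficient. The ICC above 0.90 there is agreement with another device. Reliability of either kind would not exclude a mean shift with repetition.

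**Inputs from the plan.** n = 20 (5.1); two-sided alpha 0.05 (5.6); one session before surgery and three after (5.1, 5.5).

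**Assumed inputs.** No surgical effect. A practice gain δ on log sway, equal in all conditions and still present at 6 months. Visit-to-visit SD 0.2 and residual SD 0.2 on the log scale.

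**SD of the pre-to-6-month EC change.**
- One surface: √[2 × (0.2² + 0.2²)] = √0.16 = 0.40.
- Averaged over firm and foam, which halves the residual variance: √[2 × (0.04 + 0.02)] = √0.12 = 0.346, about 0.35.

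**Chance of a significant EC reduction.** For a paired t test with 19 df and critical value 2.093, the noncentrality is δ × √20 / SD. For example, 0.10 × 4.472 / 0.346 = 1.291, which gives 23.2%.

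| Practice δ (log) | Fall in sway | SD 0.346 | SD 0.40 |
|---|---|---|---|
| 0 | 0% | 2.5% | 2.5% |
| 0.02 | 2% | 4.3% | 4.0% |
| 0.05 | 5% | 8.9% | 7.7% |
| 0.10 | 10% | 23.2% | 18.5% |
| 0.15 | 14% | 45.2% | 35.7% |
| 0.20 | 18% | 68.8% | 56.4% |

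**Cross-check on the time effect.** A simulated one-group ANOVA on time (n = 20, four visits, Greenhouse-Geisser, 4,000 runs) used between-visit correlations of 0.60, 0.75 and 0.90, also assumed. With no practice it rejects in 4% to 5% of runs. With practice of 0.2 baseline SD it rejects in 13%, 19% and 45%; with 0.3 SD, in 26%, 41% and 84%. For a given shift in baseline SDs, higher reliability makes a false attribution more likely.

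**Regression to the mean.** The expected shift is (1 − r) × the baseline deviation.
- If patients enter 0.5 SD worse than usual, sway falls by 0.20, 0.13 and 0.05 SD at r = 0.60, 0.75 and 0.90.
- Patients are recruited at surgical scheduling (5.2), not on a VETS score, and the balance criteria in 5.4 remove the worst balance. If they removed the worst 10% on sway, the baseline mean would be 0.195 SD low, and later sway would rise by 0.08, 0.05 and 0.02 SD.

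**What an EC-minus-EO contrast would do.** The visit effect cancels. The SD is √(4 × 0.04) = 0.40 on one surface, or √(4 × 0.02) = 0.28 averaged over surfaces.
- Equal practice in EC and EO: false rejection towards benefit stays at 2.5% on the log scale. This follows from the assumption and is not evidence for it.
- EC practice exceeding EO practice by 0.10 log: false rejection is about 18% at SD 0.40 and 32% at SD 0.28.
- Raw scale: proportional practice does not cancel. If EO sway is 1 unit and EC sway is 2 to 3 units (assumed; section 2.0 says only that closing the eyes increases sway), a uniform 10% fall shrinks the EC-minus-EO gap from 1 to 0.9, or from 2 to 1.8.

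**The case against.** The strongest reply is that the operative text is already modest. Aim 2 and 5.6 both describe change after surgery, so only one Abstract clause and one hypothesis go too far. That is right, and it limits the correction to those two places plus a stated limitation.

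Second, this is a pilot sized by feasibility ("a total sample size of 40 veterans is considered a realistic and achievable enrollment to generate pilot data"), and an uncontrolled pre-post arm is a visible choice. That argues against demanding a new arm. It does not make the causal wording supportable.

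Third, 5.6 read as a whole appears to keep the visual and surface factors when time is added, so a time-by-visual interaction is already in the model. That stands. What is missing is any statement that this interaction bears on Hypothesis 4, and on what scale.

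A reader might go further and infer that the design is biased in favour of surgery, with practice and regression to the mean counted as benefit. The documents do not support that. They give no size for practice. Selection is not on VETS, and the balance criteria push the other way. Section 2.0 calls CSM progressive, so untreated drift could mask a real benefit.

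A reader might also want the EC-minus-EO contrast to be a condition for any claim. The unequal-practice figures show why it should not be. Section 2.0 also reports greater sway in CSM with eyes open as well as closed, so the contrast could discard genuine improvement common to both.

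**Conclusion.** The point holds as a limit on attribution. Surgery, repeated testing and natural course are fully confounded in Aim 2, and the Abstract clause and Hypothesis 4 claim more than the design can show. The net direction of bias is unknown, and regression to the mean is a minor possibility.

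The size depends on quantities the plan does not give. Uniform practice of 0.10 to 0.20 log would produce a significant EC reduction with no surgical effect in roughly 18% to 69% of trials. At 0.02 to 0.05 log the figure is about 4% to 9%, little above nominal. These rates rest on the assumed SDs of 0.35 to 0.40, on practice lasting to 6 months, and on a pre-to-6-month EC comparison that the plan does not itself name. They illustrate vulnerability and do not predict the study's error rate. The confounding depends on none of them.

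**What to change.** 1. Reword the Abstract clause and Hypothesis 4 to match Aim 2: the study describes change in VETS scores after surgery, and COP sway in EC conditions is expected to be lower after surgery than before.
2. State in 5.6, and in any report, that the design does not separate surgery from practice or natural course.
3. In 5.6, name a supportive contrast within the time-by-visual interaction: the change in log EC sway minus the change in log EO sway on the same surface, with the visit at which it is read. Use it alongside any claim of EC-specific improvement, not as a mandatory gate.

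The cost is wording and one contrast on data already planned. The contrast cancels only practice common to EC and EO, and it misses improvement shared by both.

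Retesting the 20 controls at three visits would add 60 sessions. It would cancel practice common to the two groups but would not address natural course. For one pre-post contrast at 80% power, the detectable extra change in CSM would be about 0.81, 0.64 and 0.41 SD at r = 0.60, 0.75 and 0.90. The one-group contrast detects 0.59, 0.47 and 0.30 SD, but of total change. The corrected wording does not depend on that addition.
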